7.0 Data and Specimen Banking

No specimens will be collected.

Data will be stored initially in a secure electronic survey (e.g. Qualtrics, which is an ISO 27001 certified secure server, see <https://www.qualtrics.com/security-statement/>) server

PROTOCOL TITLE: Providing Expanded Continuous Labor Support to Pregnant Women in New Mexico with Substance Use Disorders

and ultimately at XXX on the secure server. This data will all be stored in a de-identified state. See 11.3 for more data security information. Some data cannot easily be collected electronically (e.g. SCID5, Timeline Followback) and these paper forms will be identified only by a unique randomly generated ID number, stored in locked file cabinets in a locked room at XXX. All data will be destroyed 7 years after the final publication from the study. Paper forms will be shredded at this time. Digital/electronic data will be deleted at this time as well. Identifiers will be stored in locked file cabinets in locked rooms. Links between identifiers and the study ID number will only exist in a database stored on the XXX secure server at XXX. Identifiers and links between identifiers and PHI will be destroyed at the close of the study with the IRB.

Doulas and medical staff will not identify patients as participants in this study in any of their notes or medical records nor will they record study ID numbers.

8.0 Data and Specimen Management

Data Analysis

Given the small scale of the pilot study, statistical analyses are intended to detect a signal rather than between-group differences. Preliminary analyses will focus on the distributional characteristics of the primary outcomes, in addition to conducting analyses for group baseline equivalency and participant attrition. Preliminary analyses will also examine group differences in demographics (e.g. age, education, gestation) at baseline. We will examine distributions using standard tests to detect outliers. For outcomes only measured at a single time point, analyses will consist of ANOVAs and Chi Square tests. For between-group contrasts ($df=1$) for measures expected to change over time (measured at baseline and PPFU) we will utilize the ANCOVA analog using multilevel modeling with outcome measures separately entered as a level 1 variable and group membership entered in level 2, with no protection for type 1 error. Meta analytic techniques⁴⁵ using mixed-model regressions will be used to determine overall impact of the intervention (all dependent variables entered into 1 distribution). The Q statistic will then be used to examine the homogeneity of the observed effect sizes associated with outcomes. Finding of heterogeneity will indicate that, on average, one or more outcomes are more sensitive to detecting treatment effects than others. Thus, we will identify those outcomes which provide the strongest signal. Given the nature of this rich dataset, many important analyses not directly tied to aims will be conducted (e.g. temporal patterns of relapse).

Power Analysis

Given the novelty of this pilot study, meaningful estimates of between group differences cannot be reasonably obtained or calculated. In fact, the objective of this study is to derive those estimates necessary for a future sufficiently powered R01 proposal.

Steps that will be taken to secure the data to maintain confidentiality

Most data will be collected electronically through a survey tool, such as Qualtrics. Some data are difficult to entirely collect this way (e.g. Timeline followback, SCID5) and will thus need to have values extracted from paper questionnaires or notes. Electronic data

PROTOCOL TITLE: Providing Expanded Continuous Labor Support to Pregnant Women in New Mexico with Substance Use Disorders

will be stored on a secure database. Paper records will be locked in a file cabinet in the locked offices of the PI or RA at XXX, which are co-located in a locked suite. Papers with participant names or any PII will be stored separately (in a folder for consent forms and locator forms) from other data in locked file cabinets in the PI or RA offices. These paper forms with identifying data will not contain ID numbers. The only link between ID numbers and identifying data will be on the XXX secure server in a password protected file separately from any other XXX data. Only study staff will have access to this folder. All files with ID-coded de-identified data will be password protected.

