3.0 Study-Wide Number of Subjects

We plan to enroll 34 women in order to have a final number of 30 who complete the study.

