6.0 Procedures Involved*

We will offer doula services at no cost to the 15-17 women (G1) who screen into the study and have a comparison group of 15-17 women with no doulas (TAU).

We will recruit 30-34 pregnant women (to have a final sample size of 30 women) at the XXX Program. Women in G1 will be assigned a doula. The 2nd group (G2

PROTOCOL TITLE: Providing Expanded Continuous Labor Support to Pregnant Women in New Mexico with Substance Use Disorders

Treatment as Usual) will be asked if they would potentially be interested in doula care, but will not be assigned a doula. We will conduct baseline (covariates/ dependent variables) and postpartum (outcome variables) behavioral health assessments, as well as a chart review (outcome variables and covariates).

Assessment. All questionnaires are well-validated and will be administered electronically (e.g. Qualtrics) or on paper. Baseline assessment will immediately follow screening and consent at the XXX Clinic, unless participants request more time to review the consent form or can't stay at the Clinic that day. In this case, a follow-up appointment will be made to conduct consent and/or assessments, which may then occur at the XXX Clinic or at XXX. Follow-up outcomes will be assessed at postpartum follow-ups (PPFU), ideally in the XXX Clinic, but when necessary at XXX, via the telephone, or via an online form and also by chart review. See Chart Review section below for details. Additionally, doulas will fill out a doula satisfaction survey online following each 2-week postpartum doula visit. Participants will be asked to provide a list of “locators” – people who will be able to help us find them if we lose contact before the PPFU visit. We will use a “Locator” form developed by XXX for this. This information will be stored with PII, separate from all PHI and ID numbers.

Table 1. Purpose – Measure	Baseline	2-wk PPFU
Screener – Study specific form	X	
Traumatic Life Events – Life Events Checklist - 5 ³⁸	X	X
Prenatal PTSD – PTSD Checklist - 5 ³⁹	X	X
Perinatal Depression – Edinburgh Postpartum Depression Scale ⁴⁰	X	X
Substance Use Disorders – Structured Clinical Interview for DSM5-E ⁴¹	X	
Demographics – Study specific form	X	
Current substance use – Timeline Followback ⁴²	X	X
Social Support – NIH Toolbox ⁴³	X	X
Labor & Delivery Autonomy- Mother’s Autonomy in Decision		X
Participant Satisfaction – Study specific form		X
Breastfeeding intent/uptake – Study specific form	X	X

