17.0 Number of Subjects

We will recruit up to 34 participants in order to have 30 who complete the study. We plan to recruit 17 participants for each group in order to have 15 who complete the study in each group.

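### Section 8.0 plans a baseline equivalency analysis that 15-17 women per group cannot support, and leaves single-time-point outcomes unadjusted for baseline differences

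*Combined protocol and SAP*

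**What the plan says.** The Data Analysis part of Section 8.0 opens with preliminary analyses of outcome distributions, "in addition to conducting analyses for group baseline equivalency and participant attrition". It adds: "Preliminary analyses will also examine group differences in demographics (e.g. age, education, gestation) at baseline". It states no equivalence margin, test, significance level or criterion for acceptable balance, and no action if the groups differ.

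On the outcome analyses it says: "For outcomes only measured at a single time point, analyses will consist of ANOVAs and Chi Square tests". No covariates are named for these. Measures taken at both baseline and the postpartum follow-up get a multilevel version of ANCOVA, "with no protection for type 1 error"; Section 8.0 names no further covariates there either. Section 6.0 does describe the baseline assessment and the chart review as sources of covariates.

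On group size, Section 17.0 says: "We plan to recruit 17 participants for each group in order to have 15 who complete the study in each group". On how the groups are formed, Section 6.0 says: "We will offer doula services at no cost to the 15-17 women (G1) who screen into the study" and "Women in G1 will be assigned a doula". The documents describe neither randomisation nor any other method of assignment.

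The Power Analysis part of Section 8.0 gives the purpose of the estimates: they are to inform a later, adequately powered R01 application. Aim 2(d) in Section 1.2 likewise asks for effect sizes.

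**The concern.** An analysis for equivalency with no margin has no defined result. The easiest way to complete it is to run difference tests, find nothing significant and write that the groups were equivalent at baseline. In groups this small, a non-significant difference says little about comparability.

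This matters more because random allocation is not described, so systematic differences between doula and comparison women cannot be set aside as chance. Section 5.0 lists neonatal abstinence syndrome and length of NICU stay as primary outcomes. They can have no baseline value, so even an analysis that conditions on each measure's own baseline cannot help them. Any imbalance in a prognostic characteristic passes straight into their unadjusted contrasts, and from there into the effect sizes meant for the R01.

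**Working it through.** **Inputs from the documents.** 17 women recruited and 15 completing per group (Section 17.0). These agree with Section 3.0: 2 × 17 = 34 enrolled and 2 × 15 = 30 completing, an implied loss of 4/34 = 11.8%. No alpha, SD, effect size or power is stated, so there is no power figure of the plan's own to reproduce.

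**Inputs assumed.** Two-sided alpha of 0.05 (0.10 and 0.20 as a range); true baseline imbalance of 0.5 SD (0.3 and 0.8 as a range); a 0.5-SD equivalence margin for illustration.

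**1. Can equivalence be shown?** The standard error of a standardised difference is √(2/n): 0.365 at n = 15 and 0.343 at n = 17. The usual equivalence test at 5% requires the 90% confidence interval to lie inside the margin. Its half-width is t(0.95, 2n−2) × √(2/n):

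- n = 15: 1.701 × 0.365 = 0.62 SD
- n = 17: 1.694 × 0.343 = 0.58 SD

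Both exceed 0.5 SD. The interval would breach a 0.5-SD margin even if the two observed means were identical.

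**2. What would a difference test miss?** Miss rate = 1 − power of a two-sample t test, from the noncentral t distribution with noncentrality 0.5/√(2/n), which is 1.37 at n = 15 and 1.46 at n = 17.

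| True imbalance | Alpha (two-sided) | Missed, n = 15 | Missed, n = 17 |
|---|---|---|---|
| 0.5 SD | 0.05 | 73.8% | 70.7% |
| 0.5 SD | 0.10 | 62.0% | 58.5% |
| 0.5 SD | 0.20 | 46.9% | 43.4% |
| 0.3 SD | 0.05 | 87.5% | 86.4% |
| 0.8 SD | 0.05 | 43.8% | 38.1% |

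At alpha 0.05 the 95% confidence half-width is 0.75 SD (n = 15) or 0.70 SD (n = 17), so an observed difference up to that size is non-significant. Power of 80% needs a true imbalance of 1.06 or 0.99 SD. Detecting 0.5 SD with 80% power would take about 63 women per group.

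**3. What could an imbalance do to an unadjusted contrast?** For a covariate correlated r with the outcome within groups, the bias is r × imbalance. With r = 0.5 assumed (range 0.3-0.7) and a 0.5-SD imbalance, it is 0.5 × 0.5 = 0.25 SD (0.15-0.35). Restricting to studies of 15 per group in which the baseline test is non-significant, simulation gives a mean remaining bias of 0.17 SD (0.10-0.24). A non-significant check lowers the expected bias but does not remove it.

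**The case against.** The strongest reply is that the defect is inferred. Section 8.0 names no test for the baseline step and no rule that non-significance means equivalence; it ties ANOVA and chi-square to outcomes measured once. Baseline equivalency is often shorthand for a baseline table. This stands, and it limits the point to an unspecified analysis that invites a wrong conclusion.

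It is also fair that the check gates nothing. The same contrasts are reported whatever it shows, and any bias comes from how the groups are formed. A reader might infer that the check is the plan's chief protection against confounding; the text calls it preliminary and gives it no such role.

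The multilevel ANCOVA may partly cover PTSD, depression, substance use and social support, if it conditions on each measure's own baseline. It does not cover other characteristics or single-time-point outcomes.

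A reader might extend the argument to attrition, which shares the sentence. The documents do not support that: equivalency attaches to the baseline comparison, Aim 1(e) treats attrition as a feasibility estimate, and no between-group attrition test is specified.

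Finally, this is a feasibility pilot that disclaims power and says it looks only for a signal. That caution is attached to the analyses because of the study's small scale; nothing warns specifically against an equivalency conclusion. The effect sizes are still intended for planning, where bias matters.

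**Conclusion.** The point holds in a conditional form. At 15-17 women per group, equivalence within 0.5 SD cannot be established, because the 90% confidence half-width is 0.58-0.62 SD. That result needs only the group sizes, the usual 5% equivalence test and the illustrative margin. The 71-74% miss rate needs two further assumptions, a two-sided 5% t test and a true 0.5-SD imbalance; it falls to 59-62% at alpha 0.10, and larger imbalances are caught more often.

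It would go too far to say that the plan will declare the groups equivalent on a non-significant test, or that the check causes bias. What the documents support is a risk of false assurance, together with effect sizes for single-time-point outcomes that have no planned adjustment for confounding. The bias figures of 0.15-0.35 SD are illustrations under assumed correlations.

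**What to change.** In Section 8.0, replace the baseline equivalency analysis with wording such as:

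> Baseline characteristics will be summarised by group, with standardised differences and 95% confidence intervals. Absence of a significant difference will not be taken as evidence that the groups are equivalent. For every outcome, including those measured once, the unadjusted contrast will be accompanied by an estimate adjusted for one or two prognostic baseline covariates, named here before outcome data are examined.

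The covariates should be ones already collected; baseline substance use and gestation at baseline are candidates for the sponsor to consider. For binary outcomes in about 30 women, one covariate is safer than two.

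Do not select covariates by an observed-imbalance threshold. A cut-off of 0.25 SD would be crossed by chance for 47-50% of truly balanced continuous variables at this size, and would still miss a true 0.5-SD imbalance about 22% of the time.

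The cost is a wording change and a few extra models on data already collected. Each covariate uses one residual degree of freedom (30 − 2 = 28, falling to 27 or 26 with 15 per group), so some precision may be lost. The report also gives up any statement that the groups were equivalent. Adjustment for one or two covariates will not remove all confounding, and how women are assigned to the groups remains to be described.

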5.0 Study Endpoints

Primary Outcomes

Relapse will be defined as percent drinking or drug use days postpartum and by drug screen at hospital admission results.

Postpartum PTSD severity – PTSD Checklist score

Postpartum depression severity – Edinburgh Postpartum Depression Scale Score

Breastfeeding Uptake

Neonatal Abstinence Syndrome

Length of NICU Stay

Secondary Outcomes

Social Support – NIH Toolbox

Labor and Delivery Autonomy

Participant Satisfaction

Doula Satisfaction

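### Breastfeeding uptake, a primary outcome, is assigned to neither analysis rule in section 8.0, and neither rule uses the baseline breastfeeding intent already collected as its covariate

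*Combined protocol and SAP*

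**What the plan says.** Section 5.0 lists "Breastfeeding Uptake" among the primary outcomes, without a definition, scale or time point. Aim 2 in section 1.2 includes estimating it, along with effect sizes.

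Table 1 in section 6.0 has a single row, "Breastfeeding intent/uptake – Study specific form", marked at baseline and at the 2-week postpartum follow-up (PPFU). Intent is therefore recorded before birth and uptake after it.

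The Data Analysis part of section 8.0 offers two rules:
- Single-time-point outcomes: "For outcomes only measured at a single time point, analyses will consist of ANOVAs and Chi Square tests".
- Measures expected to change and taken at both visits: "we will utilize the ANCOVA analog using multilevel modeling with outcome measures separately entered as a level 1 variable and group membership entered in level" (the upper level).

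It does not say which rule covers breastfeeding, and neither rule names a covariate. Two other statements bear on the point. Section 6.0 says "We will conduct baseline (covariates/ dependent variables) and postpartum (outcome variables) behavioral health assessments", without tying any baseline variable to any outcome. Section 8.0 plans a check of baseline equivalency and adds: "Preliminary analyses will also examine group differences in demographics (e.g. age, education, gestation) at baseline". It does not say what follows if the groups differ.

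**The concern.** Intent is the one baseline variable collected specifically for this outcome, and it is plausibly a strong predictor of uptake. The plan leaves its role open, and both available rules handle it poorly.

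- **Single-time-point rule.** Uptake can exist only after birth, so this is the natural home. A chi-square ignores intent, and any difference in intent between the groups passes into the uptake difference.
- **Baseline/PPFU rule.** The shared row in Table 1 points here. Intent is a plan and uptake is a behaviour, so intent is not a baseline value of uptake. A model that treats the two as repeated measures estimates a change with no clear meaning.

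Section 8.0 says that the study exists to supply estimates for a later, powered proposal. It also intends to pool all outcomes and pick those with the strongest signal. An uptake difference that partly reflects intent would feed both uses. Because the rule is not fixed, the choice could also be made after the data are seen.

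**Working it through.** **Inputs.** Section 17.0 gives the group size: "We plan to recruit 17 participants for each group in order to have 15 who complete the study in each group". So n = 15 per group is used. The plan states no breastfeeding rate and no power figure, so it has no number of its own to reproduce. The rates below are assumptions:
- share intending to breastfeed, q: 0.60 to 0.80
- uptake among intenders, a: 0.75 to 0.85
- uptake among non-intenders, b: 0.20 to 0.40

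**1. Variance in uptake explained by intent.** With p = qa + (1 − q)b, R² = (a − b)² q(1 − q) / [p(1 − p)].
- Lowest corner (q = 0.8, a = 0.75, b = 0.4): p = 0.68; R² = 0.1225 × 0.16 / 0.2176 = 0.09.
- Highest corner (q = 0.6, a = 0.85, b = 0.2): p = 0.59; R² = 0.4225 × 0.24 / 0.2419 = 0.42.

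**2. Gain in precision.** Simulated with no doula effect, 15 per group, unadjusted against Mantel-Haenszel risk difference stratified by intent:
- Lowest corner: standard error 0.171 falls to 0.165, about 3%.
- Highest corner: 0.180 falls to 0.139, about 23%. The 95% half-width goes from 1.96 × 0.180 = 0.35 to 1.96 × 0.139 = 0.27.

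**3. Chance imbalance, if allocation were random.** For two independent binomial counts out of 15, the probability of a gap of three or more intending women is 0.35 at q = 0.6 and 0.25 at q = 0.8.

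**4. Shift from a gap of exactly three.** (3/15) × (a − b) is 0.2 × 0.35 = 0.07 to 0.2 × 0.65 = 0.13. That is 7 to 13 points with no doula effect, and more for a wider gap.

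**5. Weak predictor.** With a = 0.7, b = 0.5 and q = 0.6, R² = 0.04 × 0.24 / (0.62 × 0.38) = 0.04. The simulated standard deviation is 0.177 with or without adjustment.

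**6. Systematic imbalance.** Suppose intent is 80% in one group and 50% in the other, with no doula effect. The expected unadjusted difference is 0.30 × (a − b). False-positive rates are simulated at an assumed two-sided 0.05, with a linear model on group and intent as the adjusted analysis:

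| Uptake with / without intent | Unadjusted difference | False positives, unadjusted | False positives, adjusted |
|---|---|---|---|
| 85% / 25% | 0.18 | 18% | 4% |
| 80% / 40% | 0.12 | 11% | 5% |
| 70% / 50% | 0.06 | 7% | 5% |

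The adjusted difference is about zero in all three. Intent is the only source of imbalance in this simulation.

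**7. Sparse cells.** At q = 0.8, about 15 × 0.2 = 3 non-intenders are expected per group. The chance that at least one group has none is 1 − (1 − 0.8¹⁵)² = 0.07. The expected count of women without uptake per group also falls below 5 once overall uptake exceeds about 67% (15 × 0.33 = 4.95), which strains a plain chi-square as well.

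**The case against.** The strongest reply is that the plan may already intend the adjustment. Its second rule is called an ANCOVA analog, and ANCOVA ordinarily conditions on the baseline value. Section 6.0 labels baseline assessments partly as covariates, and a baseline equivalency check might reveal an imbalance in intent. This is also a 30-completer feasibility study that looks for a signal, declines a power calculation and draws no confirmatory conclusion. It will be imprecise either way.

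Part of this stands. A reader might infer that the plan assigns uptake to an unadjusted chi-square. It does not: that route is an inference from when uptake can be measured. Nor does the wording prove that the multilevel model would treat intent and uptake as two waves; it only permits that reading. The size of the gain is conditional on rates that the documents do not give, and the form that records intent is not shown, so intent may not be binary.

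The rest does not answer the point. An ANCOVA on baseline presupposes the same measure at both visits, and intent is not that. The general label in section 6.0 links no covariate to uptake, and the equivalency check triggers no adjustment. A pilot whose stated product is effect-size estimates has reason to estimate them well.

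**Conclusion.** The point holds as an unassigned analysis and an unused covariate for a primary outcome. Under the assumed rates, intent explains about 9% to 42% of the variance in uptake, and adjustment cuts the standard error by about 3% to 23%. A gap of three or more intending women, expected in 25% to 35% of random allocations, shifts the uptake difference by at least 7 to 13 points across those rates. With a weak predictor the precision gain is near nil.

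A reader might also infer that adjusting for intent would make the two groups comparable. The documents do not support that. Section 6.0 describes a doula group and a comparison group without stating any randomisation. Adjustment reduces bias from an imbalance in intent but leaves other confounding in place, and the chance-imbalance figures apply only if allocation were random. The change is worth making because it costs almost nothing; it would not make the pilot precise.

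**What to change.** Add to the Data Analysis part of section 8.0 wording to this effect: breastfeeding uptake at the 2-week PPFU is a single-time-point outcome, compared between groups as a risk difference with 95% confidence interval, adjusted for baseline breastfeeding intent by a small-sample method; intent is a covariate only and is not a repeated measure of uptake. Suitable methods are Firth logistic regression with standardisation or, if intent is recorded as binary, a Mantel-Haenszel risk difference. Show the raw 2x2 table and unadjusted difference beside it. State in the same place what counts as uptake, since section 5.0 does not.

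The cost is a few lines of text and one degree of freedom, with no new data and no change in sample size. The downside is sparse non-intender strata when intent is high, and a slight loss of precision if intent is a weak predictor: with intent at 80% against 50% and uptake at 70% against 50%, the simulated standard deviation rose from 0.178 to 0.187.

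### The admission drug screen, one of two relapse measures, falls to an unadjusted chi-square although baseline use is collected, so baseline differences in use enter its effect size

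*Combined protocol and SAP*

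**What the plan says.** Section 5.0 lists relapse first among the primary outcomes and gives it two measures: "Relapse will be defined as percent drinking or drug use days postpartum and by drug screen at hospital admission results". It states no weights and no rule for combining them.

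Section 8.0 (Data Analysis) has two rules for group comparisons.
- Repeated measures: "for measures expected to change over time (measured at baseline and PPFU) we will utilize the ANCOVA analog using multilevel modeling".
- Everything else: "For outcomes only measured at a single time point, analyses will consist of ANOVAs and Chi Square tests".

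Table 1 in section 6.0 marks "Current substance use – Timeline Followback" at both baseline and the 2-week follow-up, so postpartum use days fall under the first rule. The admission screen is taken at neither visit and falls under the second. That assignment is inferred: section 8.0 does not name the screen or give its coding.

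Section 6.0 does intend baseline data to serve as covariates: "We will conduct baseline (covariates/ dependent variables) and postpartum (outcome variables) behavioral health assessments". No text applies a covariate to an outcome measured once. Section 20.0 sends chart-review data to the same analyses and adds no adjustment. Section 8.0 plans a check of baseline equivalence but states no action if the groups differ.

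**The concern.** The two measures of one primary outcome are analysed on different footings: one conditions on baseline use and the other does not. Substance use before enrolment is an obvious candidate predictor of a positive screen at admission. Section 6.0 schedules only one doula visit before labor support, so the screen should largely reflect prenatal use.

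With about 15 women per group, sizeable differences in baseline use are to be expected even under random allocation. Section 6.0 says only that women in the first group are assigned a doula, so systematic differences cannot be excluded either.

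The effect size is the product of this pilot. Section 8.0 pools all outcomes into one distribution, tests their homogeneity, looks for the outcomes with the strongest signal, and intends the estimates for a later powered proposal. A baseline difference in use could make the screen look like a strong or a weak signal for reasons unrelated to the doula.

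**Working it through.** **The plan's own figures.** Section 17.0: "We plan to recruit 17 participants for each group in order to have 15 who complete the study in each group". Thus 2 × 17 = 34 enrolled and 2 × 15 = 30 completing, which agrees with section 3.0. No alpha, power or effect size lies behind these numbers, so there is no power calculation to reproduce.

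**Inputs.**
- n = 15 per group (section 17.0).
- p = 0.5 positive. This is an assumption: section 1.1 gives about 50% as background relapse in pregnancy, not as a rate for the admission screen. p = 0.2 is shown as well.
- r, the within-group correlation between baseline use and a positive screen. This is an assumption; the documents give none, so a range is shown.

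**Raw precision.** SE of the risk difference = √(p(1−p) × 2/n) = √(0.25 × 2/15) = 0.183. The 95% half-width is 1.96 × 0.183, about 36 points.

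**Shift from chance imbalance.** Under random allocation, chance imbalance in baseline use moves the raw risk difference with SD = r × 0.183.

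**Precision after adjusting for one covariate.** Variance ratio = (1 − r²) × (1 + 1/(2n − 4)) = (1 − r²) × (1 + 1/26).

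| r | SD of chance shift (points) | Variance ratio | Adjusted SE |
|---|---|---|---|
| 0 | 0 | 1.038 | 0.186 |
| 0.2 | 3.7 | 0.997 | 0.182 |
| 0.3 | 5.5 | 0.945 | 0.177 |
| 0.5 | 9.1 | 0.779 | 0.161 |

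Break-even is where (1 − r²) × 27/26 = 1, so r² = 1/27 and r is about 0.19. Below that, adjustment costs a little precision. At p = 0.2 the raw SE is 0.146 and the chance shifts are 4.4 points (r = 0.3) and 7.3 points (r = 0.5).

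A simulation with a normal covariate and no true effect (40,000 trials per setting, p = 0.5) gave adjusted SDs of 0.186, 0.178 and 0.162 at r = 0, 0.3 and 0.5, in line with the table.

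**Systematic difference.** Suppose the groups differ by 0.5 SD in baseline use and the doula has no effect. The expected bias in the raw risk difference is about r × √(p(1−p)) × 0.5. That is 0.3 × 0.5 × 0.5 = 7.5 points, or 0.5 × 0.5 × 0.5 = 12.5 points. Simulation gave 7.5 and 12.3 points, with the adjusted estimate at about 0.

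**Power, for 50% v 20% at two-sided 5% (all assumed).** Simulated results:
- Unadjusted: 42%.
- Ordinary linear ANCOVA: 43% at r = 0.3 and 49% at r = 0.5.
- The same model with HC3 robust errors: about 40% at r = 0.3 and 45% at r = 0.5.

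**The case against.** The strongest reply is that this is a small pilot, meant by section 8.0 to detect a signal, with power analysis expressly declined. An SE of 0.16 is hardly better than 0.18 for planning. The gain rests on a correlation that the documents do not supply, and there are reasons to expect a modest one:
- Section 4.0 lets participation run from 4 to 20 weeks, so the gap between baseline and admission varies widely.
- The use-day measure counts drinking as well as drugs, while the screen is a drug screen.
- Percent use days is bounded and may contain many zeros. With an assumed 60% zeros and the latent correlation that corresponds to r = 0.5, simulated power was 47% for ordinary ANCOVA and 43% with HC3 errors, against 42% unadjusted.

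All of this stands, and it limits the claim about precision. It does not answer the point that baseline differences enter an estimate that will be pooled and reused. The equivalence check may reveal such differences but does not adjust for them.

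A reader might infer three stronger things that the documents do not support.
- *Adjustment buys a clear power gain.* With robust errors there is a small gain at r = 0.5 and a loss at r = 0.3, and both event rates are assumptions.
- *Half of the primary outcome is affected.* The screen is one of two measures, without a stated weight.
- *The groups are known to be confounded, or known to differ only by chance.* The text describes no allocation method, so neither can be asserted. If allocation is not random, one covariate deals with baseline use only.

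**Conclusion.** The point holds in a limited form. By default the admission screen gets an unadjusted comparison, a relevant baseline measure is scheduled, and nothing else in the plan adjusts for it. The main consequence is exposure of the effect size to baseline differences in use: an SD of 5.5 to 9.1 points from chance alone at r = 0.3 to 0.5 and p = 0.5, and a bias of about 7.5 to 12.3 points if the groups differ systematically by 0.5 SD.

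The precision gain is conditional: almost nil at r = 0.2, about 5% of the variance at r = 0.3, about 22% at r = 0.5, and a slight loss near r = 0. It applies to the risk difference. An adjusted log odds ratio, including a Firth estimate, does not have a smaller SE and should not be presented as a precision gain. No confirmatory conclusion is at stake. What would be affected is a planning value for the next trial.

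**What to change.** In section 8.0, take the admission drug screen out of the single-time-point rule. Analyse it by linear regression of positive screen (0/1) on group with one prespecified covariate, baseline percent use days from the Timeline Followback. Define the covariate fully, including whether drinking days count, and name the standard error to be used.

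Report the adjusted risk difference with its interval beside the raw counts and the raw risk difference, and use the adjusted estimate for effect sizes and pooling. State how it is put on the common scale. Dividing by the unadjusted within-group SD is preferable, because the residual SD would enlarge the effect by 1/√(1 − 0.25) = 1.155 at r = 0.5. State also how the groups are formed, so that readers can tell whether baseline differences are due to chance.

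The cost is a few sentences, no new data and one degree of freedom. If r is near 0, the SE rises from 0.183 to about 0.186. With HC3 errors, power for 50% v 20% goes from 42% to about 45% at r = 0.5 and to about 40% at r = 0.3. Other outcomes measured once stay unadjusted, so the pool is still not on one uniform footing.
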